10.3.4. Safety Analyses

Safety measures will include AEs, hypoglycemia, vital signs and weight, treatment exposure, laboratory measures, and antibodies to insulin lispro.

Events that are newly reported after the first dose of IP or reported to worsen in severity from baseline will be considered treatment-emergent AEs (TEAEs). The Medical Dictionary for Regulatory Activities (MedDRA) lowest level term (LLT) will be used in the treatment-emergent assessment. The maximum severity for each LLT during the baseline period will be used as baseline severity.

SAEs, AEs reported as reason for discontinuation from the IP or study, and TEAEs will be summarized in tables using the Medical MedDRA PT, sorted by decreasing frequency within the LY900014 treatment group. TEAEs will also be summarized by PT sorted by decreasing frequency within SOC for all TEAEs and TEAEs by maximum severity. For events that are specific to one sex, the denominator and computation of the percentage will include only patients from the given sex. The number and proportion of patients with at least 1 event for each type of event will be summarized and compared between treatment groups using Fisher's exact test. SAEs, AEs reported as reason for discontinuation from the study, and TEAEs will also be summarized for open-label insulin lispro during the lead-in period.

Hypoglycemia rates will be summarized for periods of 30 days, 1 year, and 100 years (severe hypoglycemia only). The rate of severe hypoglycemia per 100 years will be compared between treatment groups using the empirical method (details will be described in the SAP). For each of other categories of hypoglycemia, the number of hypoglycemia events during a specific period (rate) after randomization (for example, 0-12 weeks of treatment period) will be analyzed by using a negative binomial regression model. The model will include treatment and the baseline hypoglycemia rate (measured during lead-in) as a covariate. An offset defined as the log transformation of treatment exposure in the specific period (days)/365.25 days (or 30 days) will be included in the model to estimate the rate of hypoglycemia per year (or per 30 days). The proportion of patients with at least 1 hypoglycemic event in each category (incidence) during a specific period after randomization will be analyzed using a logistic regression model including treatment and baseline hypoglycemia rate value in the model.

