5.3. Method of Assignment to Treatment

Patients who meet all criteria for enrollment will be randomized to double-blind treatment at Visit 8. Assignment to treatment groups will be determined by a computer-generated random sequence using an interactive web-response system (IWRS). Patients will be randomized to 1 of the 2 treatment groups in 1:1 ratio (double-blind LY900014 administered at meal time, double-blind insulin lispro administered at meal time). Stratification will be by country, HbA1c stratum ($\leq 8.0\%$, $> 8.0\%$ at Visit 7), and type of basal insulin during the lead-in period (glargine U-100 or degludec [U-100 or U-200]), and number of prandial doses at study entry (< 3 , ≥ 3).

Abbreviations: T = telephone visit; wk = week.

- a At Visit 2, patients treated with insulin aspart, insulin glulisine, regular insulin, or premixed insulin will be transferred to insulin lispro. At Visit 2, patients treated with a basal insulin regimen other than insulin glargine U-100 or insulin degludec will be transferred to an allowed study basal regimen of insulin glargine U-100 once or twice daily or insulin degludec U-100 or U-200 once daily. At Visit 8, patients will be randomized to either insulin lispro or LY900014 and continue their basal insulin regimen.
- b Titrate basal insulin.
- c Titrate prandial insulin (insulin lispro or LY900014).
- d Patients will discontinue study insulins at Week 26.
- e Eligible patients will have visits at approximately 3-month intervals for up to 26 weeks after Visit 801 for follow-up of insulin lispro antibody levels.

Figure 5.1. Illustration of study design.

6. A Priori Statistical Methods

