6.2. Adjustments for Covariates

Stratification factors of this study include country, HbA1c stratum ($\leq 8.0\%$, $> 8.0\%$), type of basal insulin during the lead-in period (glargine or degludec), and number of prandial doses at study entry (< 3 , ≥ 3). Stratification factors will be entered into the IWRS for randomization and also collected in the database by electronic case report form (eCRF) or central laboratory. The analysis models will use the stratification factors as collected in the database.

For the primary analysis of HbA1c, the stratification factor of HbA1c stratum will not be included. Instead, the continuous value of baseline (Visit 8) HbA1c will be included in the analysis models.

For analyses of the incidence and rate of hypoglycemia, the baseline hypoglycemia event rate with the same category of the dependent variable will be included as a covariate in the analysis models.

Other efficacy analyses will include the stratification factors as noted in Sections 6.11 and 6.12.

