Total daily basal insulin dose, total daily prandial insulin dose, total insulin dose, and the ratio of prandial insulin dose to total insulin dose during the lead-in period will be summarized by visit for the Randomized Population. The actual and change from Visit 2 values will be compared between treatment groups using an MMRM model including the corresponding dose at Visit 2, treatment, strata (pooled country, type of basal insulin, the number of prandial doses at study entry and HbA1c stratum), visit, treatment-by-visit interaction in the model as fixed factors and patient as a random factor. Doses will be summarized in U and U/kg. Basal insulin dose will be summarized independently for glargine and degludec as well as combined.

Up to 3 OAMs (metformin, dipeptidyl peptidase-4 inhibitor [DPP-4] inhibitor, sodium-glucose co-transporter 2 [SGLT2] inhibitor, sulfonylurea, meglitinide and alpha-glucoside inhibitor) are allowed prior to the study, and up to 2 OAMs (metformin and SGLT2 inhibitor) are allowed during the lead-in and treatment periods. The proportion of patients who were treated with OAMs (by class of OAM) at each visit will be summarized and compared between treatment groups using Fisher's exact test. The number of OAMs per patient will also be summarized by treatment and by period: lead-in period (Visit 2 to Visit 8) and treatment period (Visit 8 to Visit 18).

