6.11.5. Other Secondary Efficacy Analyses

The analyses described in Section 6.11.5 to Section 6.11.7 will include data collected from all randomized patients prior to permanent discontinuation of IP. The longitudinal observations of actual and change from baseline in HbA1c up to Week 26 will be analyzed using the same MMRM model as for the analysis of the primary outcome. For the following secondary efficacy endpoints, an MMRM model similar to that for the primary outcome with an additional term of HbA1c stratum ($\leq 8\%$, $> 8\%$) will be used:

- actual and change from baseline 1,5-AG values
- actual and change from baseline 10-point SMBG values (fasting, 1 hour post morning meal, 2 hours post morning meal, pre midday meal, 1 hour post midday meal, 2 hours post midday meal, pre evening meal, 1 hour post evening meal, 2 hours post evening meal, and bedtime)
- actual and change from baseline in total, basal, and prandial insulin doses and prandial/total insulin dose ratios

Three 10-point SMBG profiles are expected to be collected during the 2 weeks prior to specified visits. Valid SMBG profiles will be used for analysis, defined as having non-missing values at ≥ 6 time points among the 10 pre-specified time points and being collected during 2 weeks prior to a given visit. For each time point, the average of the corresponding SMBG values from the valid SMBG profiles will be used for analysis. The excursion of SMBG for each meal category (that is, morning meal, midday meal, and evening meal) calculated using the average values at the corresponding time points will be used for analysis.

The following endpoints, collected from the MMTT, will be analyzed using the ANCOVA model with strata (pooled country, type of basal insulin, number of prandial doses at study entry, and HbA1c stratum) and treatment as fixed effects and baseline as a covariate:

- actual and change from baseline in fasting glucose (average of measurements at time -15 and 0), and PPG at 15, 30, 60, 120, 180, and 240 minutes after the meal
- PPG excursions at time 15, 30, 180, and 240 minutes after the meal (PPG minus fasting glucose)

Sensitivity analysis for PPG excursions may be performed to exclude patients whose PPG excursion could be affected by factors including MMTT consumption amount (for example, partial MMTT was consumed) and correction bolus insulin usage.

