A list of MedDRA PTs will be used for the narrow search of potential severe hypoglycemia in spontaneously reported AEs. The events identified through the search strategy that are also reported as SAEs will be summarized and compared between treatments. Fisher's exact test will be used to assess the treatment difference in the proportion of patients with potential severe hypoglycemia.

Table 6.6. Summary of Analyses for Endpoints Related to Hypoglycemia

Endpoint	Analysis Period	Statistical Method
Rate of hypoglycemic events (per patient per 30 days / year) 
 • All Documented^a • Nocturnal^a • Documented Symptomatic^a • Overall • Non-Nocturnal (Documented and occurred between waking and bedtime)^a • Probable Symptomatic 	0-4, 0-12, 0-26, 4-8, 8-12, 12-26 weeks	Negative binomial regression with treatment, and baseline hypoglycemia event rate with the same category of the dependent variable as covariates, log (exposure/30/365.25 days) as the offset in the model.
Incidence of hypoglycemic events 
 • All Documented^a • Nocturnal^a • Documented Symptomatic^a • Overall • Non-Nocturnal (Documented and occurred between waking and bedtime)^a • Probable Symptomatic 	0-4, 0-12, 0-26, 4-8, 8-12, 12-26 weeks	Logistic regression with treatment, baseline hypoglycemia event rate with the same category of the dependent variable as covariates.
Rate of postmeal hypoglycemic events (per patient per 30 days / year) for all 3 main meals 
 • Documented Symptomatic^a • Documented Asymptomatic^a 	≤ 0.5 , ≤ 1 , ≤ 2 , ≤ 4 , >1 to ≤ 2 and >2 to ≤ 4 hours after start of a meal within 0-12,12-26, 0-26 weeks	Negative binomial regression with treatment, baseline postmeal hypoglycemia event rate with the same category of the dependent variable as covariates, log (exposure/30/365.25 days) as the offset in the model.
Incidence of postmeal hypoglycemic events for all 3 main meals 
 • Documented Symptomatic^a • Documented Asymptomatic^a 	≤ 0.5 , ≤ 1 , ≤ 2 , ≤ 4 , >1 to ≤ 2 and >2 to ≤ 4 hours after start of a meal within 0-12,12-26, 0-26 weeks	Logistic regression with treatment, baseline postmeal hypoglycemia event rate with the same category of the dependent variable as covariates.

Summary of Analyses for Endpoints Related to Hypoglycemia

Endpoint	Analysis Period	Statistical Method

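### The negative binomial models for non-severe hypoglycemia rates omit the randomization strata; adding three of them is an optional, low-priority precision gain whose size rests on assumptions

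*SAP*

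**What the plan says.** **Randomization.** SAP 5.3 begins its list of factors "Stratification will be by country, HbA1c stratum" and continues with type of basal insulin and number of prandial doses at entry. SAP 6.2 adds that "The analysis models will use the stratification factors as collected in the database".

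**Hypoglycemia rates.** SAP Table 6.6 gives "Negative binomial regression with treatment, and baseline hypoglycemia event rate with the same category of the dependent variable as covariates", with log exposure as offset. The postmeal row has the same form, with "baseline postmeal hypoglycemia event rate with the same category of the dependent variable as covariates". SAP 6.2 sets a separate rule for hypoglycemia: "the baseline hypoglycemia event rate with the same category of the dependent variable will be included as a covariate in the analysis models". Protocol 10.3.4 agrees: "The model will include treatment and the baseline hypoglycemia rate (measured during lead-in) as a covariate".

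**Neighbouring endpoints.** Objectives 8 to 10 (1,5-AG, 10-point SMBG, insulin doses) use "an MMRM model similar to that for the primary outcome with an additional term of HbA1c stratum". Since the primary model already holds pooled country, basal type and prandial doses, all four factors are present. The ITSQ model (objective 11, SAP 6.11.6) and the PPG excursion models (SAP 6.11.2) also use all four. The HbA1c-target model (objective 12, SAP 6.11.5) and the laboratory and vital-sign models (SAP 6.12.5, 6.12.6) use none.

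**The concern.** When patients are randomized within strata that predict the outcome, a model without those strata usually leaves explainable variation in the error term. For objectives 6 and 7 the confidence interval for the rate ratio could then be wider than it need be. The covariates are already collected, and the same SAP uses them for other endpoints at the same level of the hierarchy.

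At stake is a little precision on two secondary objectives. SAP 6.5 makes no multiplicity adjustment for them, so H1 to H4 and the graphical test are untouched.

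**Working it through.** **1. The plan's own figure.** The only power statement concerns HbA1c. SE = 1.1 × √(2/284) = 0.0923; 0.4/0.0923 = 4.33; 4.33 − 1.96 = 2.37; Φ(2.37) = 99.1%. The stated figure is above 99%, so it reproduces. There is no corresponding figure for hypoglycemia.

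**2. Models compared.**
- Planned: log E(events) = b0 + b1·treatment + b2·lead-in rate + log(exposure).
- With strata: the same, plus terms for basal type, prandial doses (<3, ≥3) and HbA1c stratum (≤8.0%, >8.0%).

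**3. Inputs.** From the documents: 670 randomized 1:1, 8-week lead-in, 26-week treatment, two-sided 5% level. Completion is 568/670 = 84.8%, hence about 15% stopping early. Assumed, because the documents do not give them: event rate, dispersion, stratum splits, stratum effects and block size (4).

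**4. Simulation 1.** 6 events per patient-year, dispersion 1.5, true rate ratio 0.8, stratum effects equal in lead-in and treatment, 20,000 runs per scenario. The SE is the SD of the estimated log rate ratio across runs; percentages come from unrounded values.

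| Effect of each of three 50:50 strata | SE, planned → with strata | Change | Power, % | Size-adjusted power change, points |
|---|---|---|---|---|
| 1.0-fold | 0.0913 → 0.0913 | +0.1% | 70.1 → 70.0 | 0.0 |
| 1.3-fold | 0.0917 → 0.0916 | −0.2% | 69.1 → 69.3 | +0.2 |
| 1.5-fold | 0.0921 → 0.0917 | −0.5% | 67.5 → 68.3 | +0.6 |
| 2-fold | 0.0956 → 0.0940 | −1.7% | 63.3 → 65.7 | +1.6 |

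- With 20:80 strata at 1.3-, 1.5- and 2-fold, the SE changed by 0.0%, −0.4% and −0.9%.
- At 1.5-fold, 50:50: dispersion 0.75 gave −1.2%, dispersion 3 gave −0.1%, and 2 events per patient-year gave −0.7%.
- The model-based SE fell further than the true SE (2.7% against 1.7% at 2-fold), so it overstates the gain.
- Type I error moved by −0.06 to +0.33 point.
- Sparse events (0.1, 0.2, 0.5 per patient-year): SE +0.1%, +0.2%, −0.5%. Fitting failures were the same with and without strata (18.7%, 0.3%, 0%).

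**5. Simulation 2.** No treatment effect, 0.15 to 10 events per patient-year, two variants. Variant A used a patient frailty and the raw lead-in rate (1,600 runs per setting). Variant B was a correctly specified negative binomial model (3,000 runs), with the stratum effect acting in full beyond the lead-in rate.

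| Stratum effects | Change in true SE |
|---|---|
| 1.0 to 1.25 on each | +0.3% to −1.4% |
| One at 1.5, others null | −1.1% to −1.8% |
| All three at 1.5 | 0% to −1.0% at 0.15-1 event/patient-year; −1.7% to −2.1% at 3; −2.4% to −3.6% at 10 |
| All three at 2.0 | −1.6% to −1.7% at 0.5; −3.6% to −4.9% at 3; −4.5% to −9.9% at 10 |

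In variant B, type I error was 4.7-6.9% without strata and 4.6-6.2% with them. In variant A, where the negative binomial form is misspecified, it was 5-9% either way, so strata do not cure that.

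**6. Simulation 3 (cross-check, 1,500 runs per setting).** SE change 0.0% with no stratum effect, −0.2% to −0.9% at 1.5-fold and −1.6% at 2-fold. The mean log rate ratio was unchanged.

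**7. Meaning of a 2% lower SE.** 1/0.98² = 1.041, the equivalent of about 4% more patients. An endpoint at 80% power would rise to Φ((1.960 + 0.842)/0.98 − 1.960) = Φ(0.899) = 81.6%.

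**The case against.** **Nothing is broken.** Protocol 10.3.4, SAP 6.2 and Table 6.6 give the same model, and hypoglycemia has its own covariate rule. The lead-in rate is measured after patients move to the study basal insulin and three lispro injections a day, so it may already carry part of the basal-type and prandial-dose effects. All of this stands.

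**A stronger reading is tempting.** A reader might infer from SAP 6.2 that every model must contain the strata, so that Table 6.6 contradicts it. The text does not support this. The sentence on factors as collected in the database says which source of values to use, and the same section then prescribes the lead-in rate for hypoglycemia. Nor do the simulations show the planned test to be invalid.

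**The gain may be nil.** This stands for weak strata and sparse events, which may include the narrow postmeal windows.

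**Changing rates but not incidence breaks a symmetry in Table 6.6.** True, but there is a reason. Under a log link with randomized treatment, covariate adjustment leaves the meaning of the rate ratio essentially unchanged. An odds ratio is not collapsible, so adding covariates to the logistic models would change what they estimate.

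**Country is left out although the comparator models include it.** SAP 6.4 and 6.13.2 imply at least nine pooled levels, hence eight or more degrees of freedom. In simulation 2, adding country lowered the SE by a further 3.5 to 6 percentage points at 3-10 events per patient-year if the between-country SD of the log rate was 0.5, and by about nothing if countries did not differ. Omitting it is a judgement.

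**SAP 6.13.2 already brings in HbA1c stratum and basal type.** It does so only for documented symptomatic events, one factor at a time and with a treatment interaction. It gives no adjusted main estimate and does not cover postmeal events.

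**Conclusion.** The point holds as a free improvement of low priority. The planned rate models are valid and prespecified. Three strata that are already collected could be added with no measurable loss: the worst SE change in any setting was +0.3%, within simulation error.

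The benefit depends on quantities the documents do not give:
- about 0% if the strata are not prognostic beyond the lead-in rate, or if events are sparse;
- about 0-2% lower SE for modest effects;
- about 2-10%, in simulation 2 only, if all three strata have 1.5- to 2-fold effects at the higher event rates.

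It would be wrong to cite 0-2% as a property of this trial, or to infer any consequence for the primary or multiplicity-adjusted conclusions.

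**What to change.** In a dated SAP revision before unblinding, with the departure from protocol 10.3.4 and its reason recorded as SAP 6.1 allows:

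1. In the non-severe rate rows of Table 6.6, including postmeal, add type of basal insulin (glargine, degludec), number of prandial doses at entry (<3, ≥3) and HbA1c stratum (≤8.0%, >8.0%), as collected in the database. Keep the lead-in rate and the offset.
2. Carry the same terms into the overall hypoglycemia rate model by TEADA status (SAP 6.12.7.1) and the rate refits in SAP 6.13.2. Where a stratum is already the subgroup factor, enter it once.
3. In the Japan and MEE country analyses (SAP Appendices 2 and 3), drop any stratum that has one level or too few patients.
4. Leave the logistic incidence models and the severe-hypoglycemia analyses unchanged, and state why: adjustment changes the meaning of an odds ratio but not, essentially, that of a rate ratio.

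**Cost.** Three degrees of freedom per model and no new data. The wording change reaches many fits: ten categories × six periods, plus two postmeal categories × six windows × three periods, is 60 + 36 = 96 models. Version 3 is already approved, so this needs a further version. If unblinding has taken place, keep the planned model and label any stratified fit as post hoc.

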5.1. Overall Design

Study I8B-MC-ITRN (ITRN) is a Phase 3, prospective, double-blind, randomized, outpatient, multinational, multicenter, 2-group, parallel, active-controlled study conducted in patients with T2D currently treated with basal insulin in combination with at least 1 prandial insulin injection OR premixed insulin with at least 2 injections daily. Each of the treatment therapies, LY900014 and insulin lispro, will be administered immediately (0-2 minutes) prior to each meal in a double-blind manner. The study is designed to demonstrate noninferiority of LY900014 when compared with insulin lispro in change from baseline to Week 26 in HbA1c, when both are administered at the start of the meal. The study includes a 1-week screening period and an 8-week lead-in period, followed by a 26-week treatment period, and a 4-week safety follow-up period.

[figure not shown]
All patients who complete the 4-week safety follow-up visit (Visit 801) and have treatment-emergent insulin lispro antibodies that have not returned to the prespecified baseline range (Visit 2) will be asked to participate in follow-up to monitor insulin lispro antibody levels for up to 26 weeks after Visit 801 as described in [Appendix 8](#).

The purpose of the lead-in period (prior to randomization) will be to titrate basal insulin, obtain preliminary diagnostic laboratory tests, and determine baseline hypoglycemia rates. Patients treated with: a) basal insulin (insulin glargine U-100 or U-300, insulin degludec U-100 or U-200, insulin detemir or neutral protamine Hagedorn [NPH] insulin) in combination with at least 1 prandial injection of bolus insulin or b) at least 2 injections of premixed insulin will be eligible for inclusion in the trial. Patients should use the same study basal insulin regimen throughout the trial, with allowed regimens as follows: insulin glargine U-100 (Basaglar/Abasaglar or LANTUS) once or twice daily or insulin degludec U-100 or U-200 once daily. Patients using basal insulin regimens other than insulin glargine U-100 or degludec U-100 or U-200 will be transferred at Visit 2 to an allowed study basal insulin regimen, which will be chosen by the investigator. Basal insulin will be titrated during the 8-week lead-in period using a titration algorithm to allow the patient to reach the target fasting blood glucose (FBG) by the end of this period.

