6.2. Exclusion Criteria

Patients will be excluded from study enrollment if they meet any of the following criteria at screening:

Medical Conditions

- [15] Having any other condition (including known drug or alcohol abuse, psychiatric disorder including eating disorder) that precludes the patient from following and completing the protocol
- [16] Have been diagnosed, at any time, with T1D or Latent Autoimmune Diabetes in Adults
- [17] Have hypoglycemia unawareness as judged by the investigator
- [18] Have had any episode of severe hypoglycemia (defined as requiring assistance due to neurologically disabling hypoglycemia) within the 6 months prior to screening
- [19] Have had 1 or more episodes of diabetic ketoacidosis or hyperglycemic hyperosmolar state within the 6 months prior to screening
- [20] Have a known diagnosis of secondary diabetes (for example, diabetes caused by hemochromatosis, acromegaly, chronic pancreatitis, or pancreatectomy)
- [21] Excessive insulin resistance defined as having received a total daily dose of insulin >2.0 U/kg at the time of screening
- [22] Have a history of or are being evaluated for bariatric surgery including Roux-en-Y gastric bypass surgery, gastric banding, and/or gastric sleeve
- [23] Have cardiovascular disease, within the last 6 months prior to screening, defined as stroke, decompensated heart failure New York Heart Association class III or IV ([Appendix 6](#)), myocardial infarction, unstable angina pectoris or coronary arterial bypass graft
- [24] Renal:
 - a) History of renal transplantation
 - b) Currently receiving renal dialysis
 - c) Serum creatinine >2.0 mg/dL (177 $\mu\text{mol/L}$) at screening
- [25] Hepatic: Have obvious clinical signs or symptoms of liver disease (for example, acute or chronic hepatitis or cirrhosis), or elevated liver enzyme measurements as indicated below at screening:
 - a) Total bilirubin level (TBL) $\geq 2X$ the upper limit of normal (ULN [with the exception of Gilberts Disease]) as defined by the central laboratory,

Or

b) Alanine aminotransferase (ALT) $\geq 3X$ ULN as defined by the central laboratory,

Or

c) Aspartate aminotransferase (AST) $\geq 3X$ ULN as defined by the central laboratory

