6.12.4.1. Hypoglycemic Events

Hypoglycemia events that occur during the study outside the MMTT will be captured using an eCOA diary starting from Visit 2 through Visit 801. Whenever hypoglycemia is suspected, the patient should record the blood glucose value, any associated symptoms, and the treatment administered in eCOA. A set of events is counted as 1 event in analysis if it consists of an originating event and subsequent continuing events as marked by the patient in eCOA, or the duration between adjacent events is ≤ 30 minutes. The event with the highest severity will be selected for analysis with severity determined in the order of: 1) it is a severe hypoglycemia, 2) it has symptoms of hypoglycemia reported, and 3) it has the lowest blood glucose value. If there are multiple events tied in all 3 aspects, the event with the largest number of non-missing responses to the questions of nocturnal hypoglycemia and postmeal time frame will be selected. If there are still multiple events tied, the latest event (based on data entry time) will be selected.

The following types of hypoglycemia events will be derived in the analysis data sets: documented hypoglycemia, severe hypoglycemia, nocturnal hypoglycemia, probable symptomatic hypoglycemia, and overall hypoglycemia. Only severe hypoglycemia will be collected as AEs and all episodes of severe hypoglycemia will be considered as SAEs. Documented hypoglycemia (including documented symptomatic hypoglycemia, documented asymptomatic hypoglycemia and documented unspecified hypoglycemia) will be based on blood glucose (BG) ≤ 70 mg/dL. In addition, documented clinically significant hypoglycemia with similar criterion as above documented hypoglycemia except for the threshold of BG < 54 mg/dL will be summarized.

Table 6.6 provides detailed statistical methods for each endpoint related to hypoglycemia. For these analyses, hypoglycemia events prior to the discontinuation of IP will be summarized.

Additional analyses for other types of hypoglycemic events not mentioned in the table and for the post-treatment period may be conducted as needed.

The incidence and number of episodes of hypoglycemia during the MMTT will be summarized by treatment and time relative to the meal (≤ 0.5 , ≤ 1 , ≤ 2 , ≤ 4 , >1 to ≤ 2 and >2 to ≤ 4 hours after start of the meal) and analyzed by Fisher's exact test.

A listing of patients with at least 1 severe hypoglycemia reported (as SAE) after randomization will be provided.

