Rate of severe hypoglycemic events (per patient per year / 100 years)	0-12, 0-26, 12-26 weeks	Exposure adjusted rate per year / 100 years (calculated by total number of events divided by total exposure for individual patients) will be provided and the empirical method (see Appendix 1 for details) will be used for treatment comparison.
Incidence of severe hypoglycemic events	0-12, 0-26, 12-26 weeks	Proportion of patients with severe hypoglycemia will be reported. The treatment comparison will be based on a logistic regression model with treatment and baseline rate as a covariate.

^a All documented hypoglycemia and the subcategories based on the thresholds of blood glucose ≤ 70 mg/dL and blood glucose < 54 mg/dL will be analyzed, except for postmeal hypoglycemia for which only the threshold of ≤ 70 mg/dL will be applied.

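### Severe-hypoglycemia incidence is compared by ordinary logistic regression with no sparse-data rule, so the treatment odds ratio is infinite whenever one arm has no events

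*SAP*

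**What the plan says.** SAP Table 6.6 (section 6.12.4.1) has a row for the incidence of severe hypoglycemic events, analyzed over "0-12, 0-26, 12-26 weeks". Its method is: "The treatment comparison will be based on a logistic regression model with treatment and baseline rate as a covariate". Protocol 10.3.4 uses the same model form for incidence in every hypoglycemia category.

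SAP 6.2 defines the covariate: "the baseline hypoglycemia event rate with the same category of the dependent variable will be included as a covariate in the analysis models". SAP Table 6.2 takes baseline hypoglycemia from Visits 2 to 8, which is the lead-in. Protocol 5.1 gives its length: "The study includes a 1-week screening period and an 8-week lead-in period". On the outcome side, SAP 6.12.4.1 states that "hypoglycemia events prior to the discontinuation of IP will be summarized".

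Two exclusion criteria in Protocol 6.2 select against severe events. One is "Have had any episode of severe hypoglycemia (defined as requiring assistance due to neurologically disabling hypoglycemia) within the 6 months prior to screening". The other is "Have hypoglycemia unawareness as judged by the investigator".

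Elsewhere the SAP treats severe events as sparse. Table 6.6 compares their rate by an empirical method, not by the negative binomial model used for the other categories. For severe hypoglycemia found by a preferred-term search and also reported as a serious adverse event, Fisher's "exact test will be used to assess the treatment difference in the proportion of patients with potential severe hypoglycemia".

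The readable text gives no expected severe-event rate. It also has no rule for an arm without events or for a baseline covariate that is constant. SAP Appendix 1 and part of SAP 6.3 are blacked out, so nothing there is counted as missing.

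**The concern.** Maximum-likelihood logistic regression has no finite treatment odds ratio when one arm has no patient with an event. Patients with recent severe hypoglycemia or with hypoglycemia unawareness are excluded, and the shortest window is 12 weeks, so an empty arm is a realistic outcome. The analyst would then have to choose, after unblinding, between reporting the comparison as not estimable, dropping a term, or switching method. That choice would concern the most serious category of hypoglycemia, and one sentence written in advance would remove it.

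The covariate also attracts attention. It is an 8-week severe-event rate in patients selected for having had no such event in the 6 months before screening, so nearly every value will be zero. Whether it harms the treatment comparison is a separate question, checked in the working.

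**Working it through.** **Inputs.** 670 patients randomized 1:1 (Protocol 10.1) gives 335 per arm. The windows and model come from SAP Table 6.6, and the 8-week lead-in from Protocol 5.1. The severe-event rate is an assumption: a 26-week incidence of 0.5%, 1% or 2% in both arms, about 1, 2 or 4 events per 100 patient-years. Full exposure is assumed. Early stopping of study insulin would shorten exposure and make empty arms somewhat more frequent.

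**The plan's own figure.** The only power statement is for HbA1c: above 99% with 284 per arm, margin 0.4% and SD 1.1%. The standard error is 1.1 × √(2/284) = 0.0923. Then 0.4/0.0923 − 1.96 = 2.37, a power of 99.1%, so the figure reproduces. It says nothing about severe hypoglycemia, for which no figure is given.

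**Probability that at least one arm has no events.** With incidence p in the window, P = 1 − [1 − (1 − p)^335]². For the shorter windows, p is scaled by 12/26 or 14/26.

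Example, p = 0.005, 0-26 weeks: 0.995^335 = 0.187, and P = 1 − 0.813² = 0.34.
Example, p = 0.005 × 12/26 = 0.0023, 0-12 weeks: (1 − p)^335 = 0.461, and P = 1 − 0.539² = 0.71.

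| Assumed 26-week incidence | 0-26 weeks | 12-26 weeks | 0-12 weeks |
|---|---|---|---|
| 0.5% | 34% | 65% | 71% |
| 1% | 7% | 30% | 38% |
| 2% | 0.2% | 5% | 9% |

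These figures include trials with no event in either arm. At 0.5% incidence and 0-12 weeks that is 0.461² = 21% of trials.

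**Check by simulation.** There were 4,000 trials per setting, with Poisson events and between-patient (gamma) variance of 0, 5 or 20. At 1 per 100 patient-years an arm was empty in 34-35% (0-26 weeks) and 71-73% (0-12 weeks) of trials. At 2 per 100 the figures were 7-8% and 38-39%. At 5 per 100 they were 0.2% or less and 4-6%. At 10 per 100 they were 0.2% or less in both windows.

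**How sparse is the covariate?** The expected number of patients with a non-zero lead-in rate is about 670 × (rate/100) × 8/52. That is 0.5 patients at 0.5 per 100 patient-years, 1.0 at 1, 5.2 at 5 and 10.3 at 10. Over this range 98.5% to 99.9% of values are zero.

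**Does the covariate damage the treatment estimate?** If every lead-in rate is zero, the column is collinear with the intercept and drops out. If the few patients with a non-zero rate have no later event, the covariate's own coefficient diverges. In an example with 3 versus 6 patients with events and 335 per arm, the treatment log odds ratio is ln[(3 × 329)/(6 × 332)] = −0.70, with SE √(1/3 + 1/332 + 1/6 + 1/329) = 0.71. Both are the same to two decimals with a separated baseline covariate in the model. Fisher's p is 0.51.

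**What happens with an empty arm?** For 0 versus 4 patients, maximum likelihood diverges with or without the covariate. Firth's method gives a log odds ratio of −2.21 (SE 1.49), and Fisher's test gives p = 0.12.

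**The case against.** The strongest reply is that little depends on this row. The listed severe-hypoglycemia objective is the rate, which the empirical method compares, whereas the objectives for documented symptomatic hypoglycemia name both rate and incidence. SAP 6.5 makes no multiplicity adjustment outside the primary and multiplicity-adjusted objectives. All severe episodes count as serious adverse events, and Fisher's test is already planned on nearly the same set of events. Proportions will be reported and affected patients listed. All of this stands, and it limits the impact. It does not replace a rule: the Fisher comparison rests on a preferred-term search and has no stated 0-12 or 12-26 week split.

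The reply also notes that the event rate is assumed. Exclusion for past severe events does not fix the lead-in or treatment rate, since basal insulin is titrated during the lead-in and some patients move to three prandial injections. That stands too, and is why a range is shown.

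A reader might infer that the baseline covariate makes the comparison fail in most trials. Counting every constant or separated covariate as well as every empty arm, the 0-26 week share in the simulation is 93-100% at 1 per 100 patient-years, 72-98% at 2, 21-88% at 5 and 1-62% at 10. These shares do not measure failure of the treatment comparison. Most of them are trials in which only the covariate's coefficient is lost, except at the lowest rates and in the shorter windows, where empty arms make up much of the count.

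**Conclusion.** The point holds as a gap in the prespecified method. The stated model gives no finite treatment odds ratio when an arm has no events, and the readable text has no fallback. If the 26-week incidence is 0.5% to 1%, this is likely enough to plan for: 7-34% of trials for 0-26 weeks and 38-71% for 0-12 weeks. At 2% it matters mainly for the shorter windows, and at about 5 per 100 patient-years or more it is rare throughout. The results assume equal incidence in the arms, a constant event rate over time and full exposure.

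The cause is the rare outcome and would be present with treatment alone in the model. The covariate is a minor matter: almost uninformative, and usually harmless to the treatment estimate. The documents do not support the inference that severe hypoglycemia would go uncompared. No listed objective and no multiplicity-controlled claim depends on this row. It is a cheap improvement, and optional.

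**What to change.** In the severe-incidence row of SAP Table 6.6, replace the logistic model with one of two methods for all three windows, fixed before unblinding:

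- Fisher's exact test with an exact confidence interval, naming the effect measure to which the interval applies. This matches the SAP's own treatment of potential severe hypoglycemia in section 6.12.4.1.
- Firth-penalized logistic regression with treatment as the only term.

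Under either option, drop the baseline-rate covariate for this endpoint. Dropping it alone would not cure an empty arm; the change of method does that. Add that if neither arm has an event, the counts are reported and no effect is interpreted.

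The cost is one table cell and the loss of adjustment for a covariate that is nearly constant. Protocol 10.3.4 uses the same model form, so the SAP should record the departure and its reason. Protocol 10.3.1 and SAP 6.1 allow this without a protocol amendment when no principal feature changes.
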